4.5.3.2 Qualitative analysis

Clinically significant laboratories

Clinically significant laboratory data will be summarized using shift tables where appropriate. For each subject, the lab values in hematology, blood chemistry and urinalysis will be flagged as “low”, “normal”, or “high” relative to the normal ranges of the central laboratory, or as “unknown” if no result is available. The categorical value in urinalysis will be flagged as “positive” (or “high”), “negative” (or “normal”), or “unknown”.

For blood chemistry and serum chemistry, shifts tables from baseline to low/high post-baseline will be presented. Shift to low includes normal to low, high to low, and unknown to low. Shift to high includes normal to high, low to high, and unknown to high. For a subject if a lab is collected multiple times at post baseline, as long as one lab value is low this subject is regarded to have “low” post-baseline for this lab parameter. Similarly, if at least one post-baseline lab value is “high” this subject is regarded to have “high” post-baseline for this lab parameter.

For urinalysis, shifts tables from baseline to high/positive post-baseline will be presented. Shift to high/positive includes low to high/positive, normal/negative to high/positive, or unknown to high/positive.

Markedly abnormal laboratory

Markedly abnormal indicate clinically significant laboratory abnormalities determined by Biogen. For hematology and blood chemistry the number and percentage of subjects with markedly abnormal laboratory post-baseline will be summarized by treatment group from the criteria in Table 7. Shifts tables from baseline to markedly abnormal post-baseline will also be summarized. For a subject if a lab is collected multiple times at post baseline, as long as one lab value is markedly abnormal this subject is counted to be markedly abnormal for this lab parameter.

Subject’s listings will also be presented for all subjects with any markedly abnormal laboratory. In the listings, each subject’s complete history from screening to last study visit for that specific laboratory test meeting the criteria will be listed.

Table 7: Criteria for markedly abnormal laboratory

Parameter name	Unit	Low	High
Hematology			
White blood cells	$\times 10^9$ cells/L	<3.0	>16
Lymphocytes	$\times 10^9$ cells/L	<0.8	>12
Neutrophils	$\times 10^9$ cells/L	<1.5	>13.5
Monocytes	$\times 10^9$ cells/L	N/A	>2.5
Eosinophils	$\times 10^9$ cells/L	N/A	>1.6
Basophils	$\times 10^9$ cells/L	N/A	>1.6
Red blood cells (RBC)	$\times 10^{12}$ cells/L	≤ 3.5	≥ 6.4
Hemoglobin - Females - Males	g/L	≤ 95 ≤ 115	≥ 175 ≥ 190
Hematocrit - Females - Males	%	≤ 32 ≤ 37	≥ 54 ≥ 60
Platelet count	$\times 10^9$ cells/L	≤ 75	≥ 700
Blood Chemistry			
Alanine aminotransferase (ALT)		N/A	> 3 x ULN

Parameter name	Unit	Low	High
Aspartate aminotransferase (AST)		N/A	> 3 x ULN
Alkaline phosphatase (ALP)		N/A	>3 x ULN
Total bilirubin		N/A	>2 x ULN
Blood urea nitrogen (BUN)		N/A	≥ 10.7 mmol/L
Creatinine		N/A	≥ 176.8 umol/L
Sodium	mmol/L	≤ 126	≥ 156
Potassium	mmol/L	≤ 3	≥ 6
Chloride	mmol/L	≤ 90	≥ 118
Bicarbonate	mmol/L	≤ 16	≥ 35
Glucose (non-fasting)	mmol/L	≤ 2.2	≥ 9.7
HbA1C	%	N/A	$\geq 6.5\%$
Calcium	mmol/L	≤ 2	≥ 3
Phosphorus	mmol/L	≤ 0.5491	≥ 1.7119
Albumin	g/L	≤ 25	≥ 100
Total protein	g/L	≤ 45	≥ 100

Liver Function Abnormalities

The number and percentage of subjects with the following potentially clinically significant liver function laboratory abnormalities:

- post-baseline ALT ≥ 3 x ULN or ≥ 5 x ULN
- post-baseline AST ≥ 3 x ULN or ≥ 5 x ULN
- post-baseline total bilirubin > 1.5 x or ≥ 2 x ULN
- post-baseline AST or ALT ≥ 3 x ULN accompanied by concurrently elevated total bilirubin ≥ 2 x ULN, where concurrent is defined as on the same day.

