1. SYNOPSIS

Protocol Title:	A Phase 2, Randomized, Double-Blind, Multiple-Dose, Placebo-Controlled Study to Evaluate the Safety and Efficacy of BIIB104 in Subjects With Cognitive Impairment Associated With Schizophrenia (CIAS)
Protocol Number:	263CS201
Version Number:	4
Name of Study Treatment:	BIIB104
Study Phase:	2
Study Indication:	Cognitive impairment associated with schizophrenia
Study Rationale:	This Phase 2 study is being conducted to evaluate the safety and efficacy of BIIB104 (0.15 and 0.5 mg doses) administered orally, twice daily (BID), for 12 weeks in subjects with CIAS who are receiving antipsychotic background therapy.
Rationale for Starting Dose and Maximum Exposure:	A maximum dose of BIIB104 0.5 mg administered BID was chosen to provide exposure within the expected clinically relevant range with mean concentration levels not exceeding stopping limits set for this study. After correction for species differences in plasma protein binding and the safety factor, BIIB104 exposure limits are 8.1 ng/mL for mean C_{max} and 122 ng•h/mL for mean AUC_{24} . This is based on the no observed adverse effect level (NOAEL) for convulsions in the rat, the most sensitive nonclinical species, which is 5× (unbound C_{max} -based) the human mean C_{max} of 8.1 ng/mL. In addition, the NOAEL for intercostal muscle degeneration/regeneration in the rat is 1× (unbound AUC -based) the human mean AUC_{24} of 122 ng•h/mL. The BIIB104 maximum exposure at steady state ($C_{max,ss}$) and $AUC_{24,ss}$ from the top dosing regimen (7.47 ng/mL and 89.5 ng × h/mL) are expected to be in the exposures that have been previously shown to be safe and well tolerated in schizophrenia patients, with approximately 90% of subjects having minimum exposure at steady state ($C_{min,ss}$) equivalent to or greater than predicted clinically efficacious total plasma concentration (C_{eff}) [2.3 ng/mL]. To minimize the overlap in exposure and allow identification of the minimum efficacious dose, a 0.15 mg BID dose was also selected. At steady state, the mean $C_{max,ss}$

CONFIDENTIAL

The information contained herein may not be used, disclosed, or published without the written consent of Biogen MA Inc.

from the low dose is expected to be equivalent to C_{eff} and within the clinically relevant range.

Study Objectives and Endpoints:

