14.2. Laboratory Safety Assessments

The following parameters will be analyzed from samples collected from subjects at the times specified in Section 5. Samples will be analyzed using Good Laboratory Practice-validated assays.

- Complete blood count including: red blood cell count, white blood cell count with differentials (neutrophils, lymphocytes, monocytes, eosinophils, and basophils), hemoglobin, hematocrit, platelets, mean corpuscular volume, mean corpuscular hemoglobin, and mean corpuscular hemoglobin concentration.
- Serum chemistry, including albumin, alkaline phosphatase, ALT, AST, BUN, bicarbonate, calcium, chloride, creatinine, creatine kinase, direct bilirubin, gamma-glutamyl transferase, glucose, lactate dehydrogenase, magnesium, phosphorus, potassium, sodium, total bilirubin, total cholesterol, high-density lipoproteins, low-density lipoproteins, triglycerides, total protein, and uric acid.
- Urinalysis, including urine protein, glucose, ketones, occult blood, and white blood cells by dipstick, with microscopic examination if indicated.
- Urine drug and alcohol testing (refer to the Study Reference Manual for complete list of drugs tested).
- At Screening Visit only: testing for human immunodeficiency virus (HIV) (to be performed based upon Investigator assessment of HIV risk factors; may be omitted if not permitted by local regulations); HbA1c, HBsAg, anti-HBc, anti-HBs, and hepatitis C antibody; and follicle-stimulating hormone (postmenopausal women only).

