4.5.3 Clinical Laboratory Data

The following laboratory safety assessments will be conducted:

- Hematology: complete blood count (CBC) including red blood cell count (RBCs), white blood cell counts (WBCs) with differentials (neutrophils, lymphocytes, monocytes, eosinophils, and basophils), hemoglobin, hematocrit, mean corpuscular volume (MCV), mean corpuscular hemoglobin (MCH), and mean corpuscular hemoglobin concentration (MCHC).
- Serum chemistry: albumin, alkaline phosphatase, alanine aminotransferase (ALT), aspartate aminotransferase (AST), blood urea nitrogen (BUN), calcium, chloride, carbon dioxide, creatinine, creatine kinase, direct bilirubin, gamma-glutamyl transpeptidase (GGT), glucose, HbA1c, lactate dehydrogenase (LDH), magnesium, phosphorus, potassium, sodium, total cholesterol, total bilirubin, high-density lipoproteins, low-density lipoproteins, triglycerides, total protein, and uric acid
- Urinalysis: including determination of the presence of urine protein, glucose, ketones, occult blood, and WBCs by dipstick, with microscopic examination if indicated

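### SAP Table 7 has no creatine kinase criterion, and the SAP omits the protocol's toxicity-grade laboratory summaries, so large creatine kinase elevations are not counted separately by arm

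*SAP*

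**What the plan says.** **Collection.** Protocol Section 14.2 includes the analyte in serum chemistry ("creatine kinase, direct bilirubin, gamma-glutamyl transferase"), and SAP Section 4.5.3 repeats it ("creatinine, creatine kinase, direct bilirubin").

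**Marked abnormalities.** For hematology and blood chemistry, SAP Section 4.5.3.2 provides that "the number and percentage of subjects with markedly abnormal laboratory post-baseline will be summarized by treatment group from the criteria in Table 7". A single qualifying post-baseline value is enough for a subject to count. A shift table and a full-history listing rest on the same criteria. Table 7 has no creatine kinase row.

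**Other laboratory reporting in the SAP.** Section 4.5.3.1 gives n, mean, SD, median, quartiles, minimum and maximum by arm and visit, changes from baseline, and listings with out-of-range values flagged. Section 4.5.3.2 adds shift tables against the central laboratory's normal range. There, a shift to high means normal, low or unknown at baseline and high at least once afterwards.

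**Protocol plan.** Protocol Section 16.4.2.2 promises a shift from baseline to the post-baseline maximum for every test by arm, and also summaries by common toxicity criteria grade. SAP Section 4.5.3 contains no grade summary, and SAP Section 4.1 limits summaries to data that the SAP itself details.

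**Why this analyte.** The protocol synopsis sets an exposure limit of "122 ng•h/mL for mean" AUC24 and says that "the NOAEL for intercostal muscle degeneration/regeneration in the rat is" 1× that limit on an unbound AUC basis. For convulsions the stated multiple is 5×, on unbound Cmax. Predicted steady-state Cmax and AUC24 for the top regimen are "7.47 ng/mL and 89.5 ng × h/mL".

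**The concern.** The protocol identifies a muscle finding in the rat as the effect behind its AUC limit, with no multiple to spare at that limit. Creatine kinase is the obvious muscle-related analyte in the panel. Yet the SAP's main device for counting subjects with large laboratory deviations passes over it, and the grade summaries that might have done the job do not reach the SAP.

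At stake is a simple end-of-trial question: how many subjects in each arm had a large creatine kinase rise? Under the SAP as written there is no pre-specified answer. A threshold chosen after unblinding would be post hoc and less credible, whichever way the result pointed.

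**Working it through.** **1. Row check of the panel against Table 7.** SAP Section 4.5.3 lists 26 serum chemistry analytes. Table 7 has 26 parameters, 10 in hematology and 16 in blood chemistry. Matching carbon dioxide to bicarbonate, all 16 chemistry rows correspond to a listed analyte, so 26 − 16 = 10 analytes have no criterion:
- creatine kinase
- direct bilirubin, gamma-glutamyl transpeptidase and lactate dehydrogenase
- magnesium and uric acid
- total cholesterol, high- and low-density lipoproteins, and triglycerides

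Creatine kinase is therefore absent from the marked-abnormality counts, their shift tables and their listings.

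**2. The margins.** The 1× itself cannot be rebuilt, because the rat exposure and protein-binding figures are not in the readable text. Taking it as stated:
- Muscle, at the AUC24 limit: 1 × 122 / 122 = 1.0.
- Muscle, at the predicted top-regimen AUC24,ss: 1 × 122 / 89.5 = 1.36.
- Convulsions, at the Cmax limit: 5 × 8.1 / 8.1 = 5.
- Convulsions, at the predicted top-regimen Cmax,ss: 5 × 8.1 / 7.47 = 40.5 / 7.47 = 5.4.

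The two margins use different exposure measures. On either footing, muscle has the narrower of the two.

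**3. What each remaining output shows.** Take three hypothetical subjects: A goes from normal to 1.1 × ULN, B from normal to 20 × ULN, and C from just above ULN to 20 × ULN.
- *SAP shift-to-high table:* A and B each count once and look the same. C does not count, because high to higher is not a shift under the SAP definition.
- *By-visit descriptive statistics:* B's or C's value can appear as the maximum, but one maximum does not say how many subjects had large values. Each window keeps only the record closest to the target day, so a higher unscheduled value in the same window drops out. The Table 7 rule would count any qualifying post-baseline value.
- *Listings:* all three values are flagged if above range, but a listing is not a count by arm.
- *Grade summaries:* these are planned by size in the protocol, without naming analytes, and are absent from the SAP.

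None of the SAP's laboratory outputs yields the number of subjects per arm with a large elevation.

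**The case against.** The strongest reply is that creatine kinase is far from ignored. Crossing ULN is counted by arm, and one high post-baseline value suffices. The descriptive statistics include the median and quartiles, which a skewed marker does not distort as it does a mean. A laboratory value that the investigator judges clinically significant becomes an adverse event (Protocol Section 15.1.1) and is tabulated by preferred term and maximum severity (SAP Section 4.5.2.1). Full examinations cover the musculoskeletal system and muscle strength, and SAP Section 4.5.6 summarizes the findings. All of this stands. A reader might infer from the missing row that a muscle signal would not be counted by arm at all; the documents do not support that.

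A reader might also take 122 ng·h/mL as a ceiling for each subject and estimate how many in the 0.5 mg arm would exceed it. That does not follow either. The limit is on mean exposure and is aligned to a no-adverse-effect level. Such an estimate would need a between-subject variability that the readable text does not give, and it would count people above an exposure, not creatine kinase elevations missed.

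Finally, Table 7 reflects the sponsor's own choice, and nine other chemistry analytes also lack a row. That is fair for the nine. Creatine kinase differs because the synopsis names a muscle effect. Table 7 also does not look tailored to this trial: it carries an HbA1c row, although Protocol Section 14.2 measures HbA1c at Screening only.

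**Conclusion.** The point holds in a limited form. Large creatine kinase elevations are not counted separately by arm, because Table 7 has no criterion and the SAP does not carry forward the protocol's toxicity-grade summaries. The second half is also a mismatch between the two documents that needs reconciling in its own right.

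The size is minor to moderate. It concerns one safety analyte, and it leaves the primary analysis, significance level and sample size unchanged. Its importance comes from the muscle margin: 1× at the exposure limit and about 1.36× at the predicted top-regimen AUC24,ss.

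The conclusion rests on two assumptions. First, creatine kinase is taken to be a useful laboratory marker of muscle injury; this is a general judgement, since no readable passage names it as the monitor for the rat finding. Second, muscle is called the narrower margin only against the one other margin in the synopsis; the redacted background may contain more.

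**What to change.** Before unblinding, do one or both of the following:
- Add a creatine kinase row to SAP Table 7 in multiples of ULN, with reporting cut-points set by the sponsor. Give it the same by-arm count, shift table and full-history listing as the other rows.
- Restore in SAP Section 4.5.3 the toxicity-grade summaries planned in Protocol Section 16.4.2.2, and name creatine kinase among the analytes.

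The first is the more direct. The second also brings the two documents into line. If only the first is adopted, the SAP should still say why the grade summaries were dropped. The cut-points serve reporting only and alter no dosing, monitoring or stopping rule.

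The cost is one table row or one added summary, with no new data collection. The downside is that some incidental elevations, for example after exercise, will be counted and listed. Protocol Section 8.3.3 limits this by asking subjects to avoid strenuous exercise for at least 48 hours before laboratory blood draws, and the comparison with placebo helps in reading what remains.

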4.5.4 Vital Signs

Vital sign parameters include temperature, systolic blood pressure, diastolic blood pressure, pulse rate, respiration rate and weight. The descriptive statistics for actual values and change from baseline will be summarized at each visit.

The analysis of vital signs will also focus on the incidence of clinically relevant outliers based on the following criteria. The incidence and percentage of clinically relevant outliers determined by each criterion will be summarized. A listing of subjects with clinically relevant vital signs will be provided.

Table 8: Criteria to determine clinically relevant abnormalities in vital signs

Variable	Low	High
Systolic Blood Pressure	<90 mmHg or > 15 mmHg decrease from baseline	>180 mmHg or > 20 mmHg increase from baseline
Diastolic Blood Pressure	< 50 mmHg or > 15 mmHg decrease from baseline	>105 mmHg or > 15 mmHg increase from baseline
Pulse*	< 50 bpm post-baseline or > 20 bpm decrease from baseline	>120 bpm post-baseline or > 30 bpm increase from baseline
Temperature	>38°C or > 1°C increase from baseline	
Respiration Rate	≤10 breaths/min post-baseline and >10 breaths/min at baseline	≥20 breaths/min post-baseline and <20 breaths/min at baseline

* bpm = beats per minute

Visit windows for by visit summaries

For vital sign by visit summaries, the analysis visit should be defined using window in the table below. If there is more than 1 value in the same analysis visit window for a certain parameter for a subject, the closest record to the target visit day will be used for the by visit analysis. If there are 2 values in the same analysis visit window with the same distance from the target visit day for a certain parameter for a subject, then the record with the later date will be used for the by visit analysis.

Table 9: Visit windows for vital sign

Analysis visit	Target visit day	Analysis visit window
Baseline	1	Most recent non-missing pre-dose value
Week 1	8	[2, 10]
Week 2	15	[11, 21]
Week 4	29	[22, 35]
Week 6	43	[36, 49]
Week 8	57	[50, 63]
Week 10	71	[64, 77]
Week 12	85	[78, EOS]

4.5.5 C-SSRS data

The Columbia Suicide Severity Rating Scale (C-SSRS) is an assessment that evaluates suicidal ideation and behavior.

There are 5 “Yes/No” questions from suicidal ideation section with the following increasing severity order: (1) Wish to be dead, (2) Non-specific active suicidal thoughts, (3) Active suicidal ideation with any methods (not plan) without intent to act, (4) Active suicidal ideation with some intent to act, without specific plan, (5) Active suicidal ideation with specific plan and intent.

From suicidal behavior section, there are 6 “Yes/No” questions with the following order: (1) Actual attempt, (2) Has subject engaged in non-suicidal self-injurious behavior? (3) Interrupted attempt (4) Aborted Attempt (5) Preparatory Acts or Behavior (6) Suicidal behavior was present during the assessment period?

The summary table for C-SSRS will include the number of subjects who answered “Yes” to one of the 5 questions in suicidal ideation section, or answer “Yes” to one of the 6 questions in suicidal behaviour section. A listing of subjects with any suicidal ideation or suicidal behaviour at baseline or post-baseline will be provided.

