16.4.2.4. C-SSRS

C-SSRS data will be summarized by each treatment group.

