2. STUDY DESIGN

2.1 Study Overview

This is a Phase 2, randomized, double-blind, placebo-controlled, parallel-group study to evaluate the safety, tolerability, and efficacy of BIIB104 in subjects with CIAS. Approximately 219 male and female subjects with stable schizophrenia from age 18 to 55 years, inclusive, will be recruited. Dosing with BIIB104 0.15 mg BID and 0.5 mg BID versus placebo BID will be evaluated over a treatment phase of 12 weeks. The study will be conducted at approximately 80 sites globally including non-English speaking countries.

The study includes a screening phase, a placebo lead-in phase, a randomized treatment phase, and a safety follow-up (SFU) phase to begin after the last dose of study treatment.

Screening evaluation will occur up to 35 days prior to randomization. Once eligibility has been established, a 7-day Placebo Lead-In evaluation will be conducted to assess the subject's ability to comply with dosing requirements. After Sponsor confirmation of eligibility and completion of baseline measurements at the Baseline/Day 1 Visit, subjects will be randomized in a 1:1:1 ratio to receive BIIB104 0.5 mg, BIIB104 0.15 mg, or placebo. Subjects will be dosed at approximately 12-hour intervals for 12 weeks. Total duration of subject participation will be approximately 19 weeks from screening to final follow-up visit.

[figure not shown]
There are 3 treatment groups and subjects are randomized in a 1:1:1 ratio into 1 of 3 treatment groups. The randomization will be stratified by region.

Table1: Treatment groups

Treatment Groups	Description
Placebo group	Up to 73 subjects to receive oral dosing BID with placebo for 12 weeks.
BIIB104 0.15 mg group	Up to 73 subjects to receive oral dosing BID with BIIB104 0.15 mg for 12 weeks
BIIB104 0.5 mg group	Up to 73 subjects to receive oral dosing BID with BIIB104 0.5 mg for 12 weeks

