4.5 Safety Analysis

4.5.1 General considerations

Analysis population

Safety population will be used for safety analyses of adverse events, clinical laboratory data, Columbia Suicide Severity Rating Scale (C-SSRS) data, ECG data and vital signs data.

Safety treatment groups

Different from efficacy analysis, for safety treatment group if a subject who was randomized to a placebo group accidentally received one or more doses of the active treatment during the study, he or she will be classed to low or high dose group based on the dose group of the active treatment received. A listing of these subjects will be provided. Safety treatment groups will be the same as the randomization treatment groups for other subjects (subjects randomized to active treatment groups, and subjects randomized to placebo without any accidental active dose). Safety treatment groups will be used for all the safety analyses unless otherwise specified.

Incidence and incidence proportion

Incidence and incidence proportion will be provided in incidence tables. Incidence is defined as the number of subjects who experienced an event. Incidence proportion is defined as the number of subjects who experienced an event divided by total number of subjects in the analysis population, i.e., percentage. Each subject will be counted only once within each category.

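### Read as an any-of count, the SAP's C-SSRS rule counts non-suicidal self-injury (item 2) as suicidal behaviour

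*SAP*

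**What the plan says.** SAP 4.5.5 sets out five ideation questions and six behaviour questions. The second and third behaviour questions read "2) Has subject engaged in non-suicidal self-injurious behavior? (3) Interrupted attempt", and the last is "6) Suicidal behavior was present during the assessment period". The summary table is to hold the number of subjects with a Yes to one of the five ideation questions, or a Yes "to one of the 6 questions in suicidal behaviour section". No item is excepted, and no row layout is given. The section ends with the listing: "A listing of subjects with any suicidal ideation or suicidal behaviour at baseline or post-baseline will be provided".

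The other analysis text adds little:

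- Protocol 16.4.2.4 says only that "C-SSRS data will be summarized by each treatment group".
- SAP 4.3.2 names the C-SSRS among the baseline variables without defining a summary.
- SAP 4.5.1 gives the general rule for incidence tables: "Each subject will be counted only once within each category".

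Protocol 14.1.4 describes the scale as an assessment of suicidal ideation and suicidal behaviour, and sends subjects with a Yes to any behavioural question after baseline for clinical assessment.

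**The concern.** The counting rule follows where a question sits on the form, not what it asks. One of the six questions in the behaviour section concerns self-injury that the SAP itself labels non-suicidal. An any-behaviour count built on all six would therefore mix that item with attempts and preparatory acts. It could also count a subject for whom the summary question, item 6, says that no suicidal behaviour was present.

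The C-SSRS is named among the secondary safety endpoints in protocol Table 6. A reader comparing arms on an aggregate behaviour row would take it to mean suicidal behaviour. Protocol exclusion criterion 37 bars subjects with a recent suicide attempt, or recent ideation with intent and a method or plan. It is therefore reasonable to expect few true events, although the documents give no rate. In a sparse row, one or two subjects are visible.

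**Working it through.** No figure in the plan needs reproducing. The check is a logical one, followed by one division.

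**Inputs**

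- Behaviour items (SAP 4.5.5): 1 actual attempt, 2 non-suicidal self-injury, 3 interrupted attempt, 4 aborted attempt, 5 preparatory acts, 6 suicidal behaviour present. Six are listed, which matches the six in the rule.
- Rule (SAP 4.5.5): Yes to one of the six.
- Arm size (SAP 2.1, Table 1): "Up to 73 subjects to receive oral dosing BID with placebo for 12 weeks", and the same for each active arm.
- Denominator for incidence tables (SAP 4.5.1): "Incidence proportion is defined as the number of subjects who experienced an event divided by total number of subjects in the analysis population".

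**Step 1: apply the rule to answer patterns.** The comparison is with a count that uses items 1, 3, 4, 5 and 6 only.

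| Answers | Counted by the SAP rule | Counted without item 2 |
|---|---|---|
| All six No | 0 | 0 |
| Item 2 Yes, the other five No | 1 | 0 |
| Item 2 Yes and at least one other Yes | 1 | 1 |
| Item 2 No and at least one other Yes | 1 | 1 |

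The two counts differ only in the second pattern. Let k be the number of subjects in an arm with that pattern. The any-behaviour count then exceeds the count without item 2 by exactly k.

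**Step 2: other possible rows.**

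- Single combined ideation-or-behaviour row: a subject already counted for ideation is not counted again. The excess is k0, where k0 ≤ k is the subset with no ideation Yes.
- One row per question: the excess is 0, because item 2 appears under its own label.

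**Step 3: size.** With 73 subjects in the arm, the excess proportion is k/73. For k = 1 it is 1/73 = 0.0137, or 1.4 percentage points. Section 4.5.5 promises only numbers of subjects, so the percentage applies only if percentages are shown. The documents do not give k, and none is assumed.

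**Step 4: which reading is more natural.** Where the SAP wants separate counts, it says so. Section 4.5.4 asks for vital-sign outliers by each criterion, and section 4.5.6 asks for examination results for each function. Section 4.5.5 says one of the five, or one of the six. That is any-of wording, but it does not settle the layout.

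**Step 5: does other text remove item 2?** Protocol 16.4.2.4 and SAP 4.3.2 give no item definition. SAP 4.5.1 governs double counting, not which items qualify. Protocol 14.1.4 sets a trigger for clinical assessment, which is not an analysis definition. None of them removes it.

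**The case against.** The best reply is that the problem depends on a table nobody has seen. Section 4.5.5 numbers and labels every question, so a count per question is a possible reading, and then nothing is mixed. This stands as a limit on the claim. It does not remove the need for a definition, because two programmers could produce different tables from the same sentence.

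A second reply is that an inclusive count is accurate to its stated rule, cannot miss suicidal behaviour, and follows the protocol's own grouping of behavioural questions. That is fair as far as it goes. However, a wide net for clinical assessment is compatible with a narrower reporting definition, and over-counting is still a wrong count if the row is read as suicidal behaviour.

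Third, other outputs help. Item 6 is collected, subject listings are planned, and positive behavioural answers after baseline are assessed for whether an adverse event occurred. If item-level answers are listed, item-2-only subjects can be found. This reduces the consequence but does not correct the table.

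Some stronger readings are tempting and are not supported:

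- **The listing has the same fault.** It is worded as suicidal ideation or suicidal behaviour, and plain reading already leaves out an item the SAP calls non-suicidal. What remains is a possible mismatch: a subject counted in the table might not be listed.
- **A pooled active-arm effect can be quoted.** A BIIB104 total column is described only for the adverse event tables (SAP 4.5.2.1). The C-SSRS is summarised by treatment group.
- **The rule distorts safety monitoring or favours an arm.** Protocol 19.2.1 names adverse event listings and laboratory results for the data monitoring committee's periodic review, and no test or decision rule uses this count. Nothing in the documents suggests that item-2-only answers would differ between arms.

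**Conclusion.** The point holds in a limited form. As an any-of count, the stated rule classes an item-2-only subject with suicidal behaviour, against the SAP's own label for that item and possibly against the same subject's answer to item 6. No other text corrects it.

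The size is one subject per occurrence, or 1.4 percentage points of an arm of 73 if percentages are shown. The total is unknown. The conclusion assumes that an aggregate behaviour count, or a combined ideation-or-behaviour count, will be produced. If the table has only one row per question, there is no effect.

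This is a low-priority correction to a descriptive safety table. It has no bearing on the efficacy analyses or the sample size.

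**What to change.** In SAP 4.5.5, state that suicidal behaviour, for any aggregate count and for consistency in the listing, means Yes to item 1, 3, 4, 5 or 6. Report item 2 on its own row, labelled non-suicidal self-injury, so that nothing is hidden.

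Two further changes are optional matters of table layout: showing ideation and behaviour on separate rows, and using the same definition for the baseline summary in SAP 4.3.2.

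The cost is one sentence, one table shell and one listing shell. No new data are needed, since all six items are already collected. The change affects reporting only and leaves the clinical follow-up in protocol 14.1.4 untouched. It is best made before unblinding, so that the definition is not chosen with the results in view.
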